10.12.6. Substudy B Intervention and Concomitant Therapy

10.12.6.1. Study Intervention(s) Administered for Substudy B

Study interventions for Substudy B will include:

Intervention Name	BNT162b2 ^a	qIRV	qIRV ^b /BNT162b2 ^a	tIRV°/BNT162b2ª	bIRV ^c /BNT162b2 ^a	QIV
Arm Name (group of participants receiving a specific study intervention or no study intervention)	Licensed QIV + BNT162b2 ^a	qIRV	qIRV/ BNT162b2ª	tIRV/ BNT162b2ª	bIRV/BNT162b2*+ licensed QIV	Licensed QIV + BNT162b2 ^a or Licensed QIV + bIRV/BNT162b2 ^a
Targeted Influenza Strains	N/A	Strains as recommended by WHO for recombinant or cell-based influenza vaccines	Strains as recommended by WHO for recombinant or cell-based influenza vaccines	Strains as recommended by WHO for recombinant or cell-based influenza vaccines	Strains as recommended by WHO for recombinant or cell-based influenza vaccines	For each seasonal strain as recommended by WHO
Туре	modRNA vaccine	modRNA vaccine	modRNA vaccine	modRNA vaccine	modRNA vaccine	Vaccine
Dose Formulation	modRNA	modRNA	modRNA	modRNA	modRNA	
Unit Dose Strength(s)	BNT162b2 ^a	participants 18 through 64 years of age (as detailed in the IPM)	μg or μg or μg or μg in dose-level combinations as described in the tables titled Substudy B: All Vaccine Groups	BNT162b2 ^a	BNT162b2 ^a	BNT162b2 ^a As detailed in the IPM
Route of Administration	Intramuscular injection	Intramuscular injection	Intramuscular injection	Intramuscular injection	Intramuscular injection	Intramuscular injection
Use	Experimental	Experimental	Experimental	Experimental	Experimental	Experimental

IMP or NIMP/AxMP	IMP	IMP	IMP	IMP	IMP	IMP
Packaging and Labeling	11 11 1	will be provided in a glass vial as open-label supply. Each vial will be labeled per country	glass vial as open-label supply. Each vial will be labeled per country	will be provided in a glass vial as open-label supply. Each vial will be	will be provided in a glass vial as open-label supply. Each vial will be labeled per country	Study intervention will be provided as either a PFS or a glass/plastic vial as open-label supply. Each PFS or vial will be labeled per country requirement.

Bivalent BNT162b2 (original*/Omi BA.4/BA.5) will be used during Substudy B. *Original refers to the ancestral strain (Wuhan-Hu-1; USA-WA1/2020), also referred to in this protocol as the reference strain.

Will have formulations that are CCI
Formulations will be CCI

per the IPM and CCI

10.12.6.1.1. Administration for Substudy B

See Section 6.1.1.

During Substudy B, participants will receive study intervention at Visit 201 as randomized in accordance with the SoA (Section 10.12.1). All study intervention should be administered intramuscularly into the deltoid muscle of the right arm, other than licensed QIV, which should be administered intramuscularly into the deltoid muscle of the left arm.

10.12.6.1.2. Medical Devices for Substudy B

See Section 6.1.2.

10.12.6.1.3. Preparation, Handling, Storage, and Accountability for Substudy B

See Section 6.2.

10.12.6.1.3.1. Preparation and Dispensing for Substudy B

See Section 6.2.1.

During Substudy B, study intervention will be prepared by qualified site personnel according to the IPM or package insert, and the study intervention will be administered in such a way as to ensure the participants remain blinded.

10.12.6.1.4. Allocation to Study Intervention for Substudy B

See Section 6.3.

Allocation of study intervention at Visit 201 in Substudy B will be conducted via the IRT.

10.12.6.2. Blinding for Substudy B

10.12.6.2.1. Blinding of Participants for Substudy B

Substudy B participants will be blinded to their assigned study intervention.

10.12.6.2.2. Blinding of Site Personnel for Substudy B

Substudy B is single-blind, such that all site personnel, including the investigator, investigator staff, and study staff receiving, storing, dispensing, preparing, and administering the study interventions will be unblinded.

10.12.6.2.3. Blinding of the Sponsor for Substudy B

To facilitate rapid review of data in real time, and to allow an assessment of safety data by study intervention group, sponsor staff will be unblinded to study intervention allocation for the participants enrolled during Substudy B.

10.12.6.2.4. Breaking the Blind for Substudy B

Not applicable.

10.12.6.3. Study Intervention Compliance for Substudy B

See Section 6.5.

10.12.6.4. Dose Modification for Substudy B

Not applicable.

10.12.6.5. Continued Access to Study Intervention After the End of the Study for Substudy B

See Section 6.7.

10.12.6.6. Treatment of Overdose for Substudy B

See Section 6.8.

10.12.6.7. Prior and Concomitant Therapy for Substudy B

For Substudy B, the following concomitant medications and vaccinations will be recorded in the CRF:

- Prior receipt of any COVID-19 vaccine.
- Prior receipt of any pneumococcal vaccine.
- Licensed influenza vaccine, if received during the 12 months prior to enrollment.
- Any vaccinations received from 28 days prior to enrollment until the last visit (Visit 204).
- Prohibited medications listed in Section 10.12.6.7.1, if taken, will be recorded and include start and stop dates, name of the medication, dose, unit, route, and frequency.

10.12.6.7.1. Prohibited During the Study for Substudy B

- Unless considered medically necessary, no vaccines other than study intervention should be administered within 14 days before and 14 days after study vaccination at Visit 201.
- Receipt of any other (nonstudy) coronavirus vaccine from enrollment throughout the entire study is prohibited.
- Receipt of any other (nonstudy) seasonal influenza vaccine from enrollment throughout the entire study is prohibited.
- Receipt of chronic medications with known systemic immunosuppressant effects, or radiotherapy, within 60 days before enrollment through conclusion of the study is prohibited.

- Receipt of systemic corticosteroids (≥20 mg/day of prednisone or equivalent) for ≥14 days is prohibited from 28 days prior to enrollment through 28 days after administration of the study intervention.
- Receipt of blood/plasma products, immunoglobulins, or monoclonal antibodies, from 60 days before study intervention administration through conclusion of the study.
- Prophylactic antipyretics and other pain medication to prevent symptoms associated with study intervention administration are not permitted. However, if a participant is taking a medication for another condition, even if it may have antipyretic or pain-relieving properties, it should not be withheld prior to study vaccination.

10.12.6.7.2. Permitted During the Study for Substudy B

- Medication other than that described as prohibited in Section 10.12.6.7.1 required for treatment of preexisting conditions or acute illness is permitted.
- Inhaled, topical, or localized injections of corticosteroids (eg, intra-articular or intrabursal administration) are permitted.

10.12.7. Discontinuation of Substudy B Intervention and Participant Discontinuation/Withdrawal

See Section 7.

10.12.8. Substudy B Assessments and Procedures for Substudy B

For participants in Substudy B, the minimal blood sampling volume is approximately 40 mL (15 mL at Visits 201 and 204 and approximately 2.5 mL at screening and Visits 201, 202, and 203). Up to 20 participants in Groups 3, 4, and 5 in the 18- through 64-year age stratum will be asked to consent to alternatively providing 50-mL, rather than 15-mL, blood samples at the same time points, which will be used for immunogenicity assessments as well as assay development.

For all participants, other additional blood samples may be taken for safety assessments, provided the total volume taken during the study does not exceed 550 mL during any period of 60 consecutive days.

10.12.8.1. Telehealth Visits for Substudy B

In Substudy B, the final visit will consist of a telehealth visit to assess participant safety and collect data points. Telehealth includes the exchange of healthcare information and services via telecommunication technologies (eg, audio, video, videoconferencing software) remotely, allowing the participant and the investigator to communicate on aspects of clinical care, including medical advice, reminders, education, and safety monitoring. The following assessments must be performed during a telehealth visit (see the SoA):

- Review and record any AEs and SAEs since the last contact. Refer to Section 8.4.
- Review and record any new concomitant medications or changes in concomitant medications since the last contact.
- Procedures as indicated for Visit 205 (Section 10.12.8.9.6).

Study participants must be reminded to promptly notify site staff about any change in their health status.

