8.4.1. Time Period and Frequency for Collecting AE and SAE Information Substudy A

The time period for actively eliciting and collecting AEs and SAEs ("active collection period") for each participant begins from the time the participant provides informed consent, which is obtained before the participant's participation in the study (ie, before undergoing any study-related procedure and/or receiving study intervention), through and including Visit 4 (4-week follow-up visit). Additionally, any AEs occurring up to 48 hours after the blood draws at Visits 4 and 5 must be recorded on the CRF.

SAEs will be collected from the time the participant provides informed consent to approximately 6 months after the participant's last study vaccination (Visit 6).

Substudy B

The time period for actively eliciting and collecting AEs and SAEs ("active collection period") for each participant begins from the time the participant provides informed consent, which is obtained before the participant's participation in the study (ie, before undergoing any study-related procedure and/or receiving study intervention), through and including Visit 204. Additionally, any AEs occurring up to 48 hours after the blood draws at Visit 204 in Substudy B (if eligible as per Section 10.12.1) must be recorded on the CRF.

SAEs will be collected from the time the participant provides informed consent to approximately 6 months after the participant's first study vaccination (Visit 205).

Follow-up by the investigator continues throughout the active collection period and until the AE or SAE or its sequelae resolve or stabilize at a level acceptable to the investigator.

When a clinically important AE remains ongoing at the end of the active collection period, follow-up by the investigator continues until the AE or SAE or its sequelae resolve or stabilize at a level acceptable to the investigator and Pfizer concurs with that assessment.

For participants who are screen failures, the active collection period ends when screen failure status is determined.

If the participant withdraws from the study and also withdraws consent for the collection of future information, the active collection period ends when consent is withdrawn.

If a participant permanently discontinues or temporarily discontinues study because of an AE or SAE, the AE or SAE must be recorded on the CRF and the SAE reported using the Vaccine SAE Report Form.

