8.4.7. Adverse Events of Special Interest

The following events are considered AESIs:

For Substudy A:

- A confirmed diagnosis of influenza.
- Confirmed diagnosis of myocarditis or pericarditis occurring within 4 weeks after vaccination. See Section 10.11.8.8.10.
- Confirmed COVID-19 diagnosis after Visit 1 through the end of the study (clinical signs/symptoms per CDC²⁸ and positive SARS-CoV-2 NAAT or rapid antigen test result).

For Substudy B:

- A confirmed diagnosis of influenza.
- Confirmed diagnosis of myocarditis or pericarditis occurring within 6 weeks after vaccination. See Section 10.12.8.12.
- Confirmed COVID-19 diagnosis after Visit 201 through the end of the study (clinical signs/symptoms per CDC²⁸ and positive SARS-CoV-2 NAAT or rapid antigen test result) (excluding Group 12).
- Potential menstrual cycle disturbances. See Section 10.12.8.11.

AESIs are examined as part of routine safety data review procedures throughout the clinical trial and as part of signal detection processes. Should an aggregate analysis indicate that these prespecified events occur more frequently than expected, eg, based on epidemiological data, literature, or other data, then this will be submitted and reported in accordance with Pfizer's safety reporting requirements. Aggregate analyses of safety data will be performed on a regular basis per internal SOPs.

All AESIs must be reported as an AE or SAE following the procedures described in Section 8.4.1 through 8.4.4. An AESI is to be recorded as an AE or SAE on the CRF. In addition, an AESI that is also an SAE must be reported using the Vaccine SAE Report Form.

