assist the participant with downloading the application or issue						
provisioned device if required						
Provide thermometer and measuring device		X				
Review reactogenicity e-diary data (daily review is optimal						
during the active diary period)		ţ		*		
Review ongoing reactogenicity e-diary symptoms and obtain stop				X	X	
dates						
Collect AEs and SAEs as appropriate ^{f,d}	X	X	X	X	X	X
Collect e-diary or assist the participant with deleting application				X	X	

- a. Visit may be completed as a home health visit (see Section 10.12.8.2).
- b. Visit will be completed as a telehealth visit (see Section 10.12.8.1).
- c. Including, if indicated, a physical examination.
- d. Prior to vaccination at Visit 201.
- e. Only up to 20 participants in Groups 3, 4, and 5 will have 50 mL drawn (see Section 10.12.4.1).
- f. AEs are collected from the completion of informed consent through Visit 204. SAEs are collected from the completion of informed consent through the end of study participation. Additionally, any AEs occurring up to 48 hours after blood draws at Visit 204 must be recorded.

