- Record any AEs that occur within the 48 hours after the blood draw as described in Section 8.4.1.

10.12.8.9.6. Visit 205 – 6-Month Telephone Contact – 175 to 189 Days After Last Study Vaccination for Substudy B

- Contact the participant by telephone.
- Record SAEs as described in Section 8.4.1.
- Record nonstudy vaccinations as described in Section 10.12.6.7.
- Record prohibited medication use as described in Section 10.12.6.7.1.
- Complete the source documents.
- The investigator or an authorized designee completes the CRFs.

10.12.8.9.7. Unscheduled Visit for a Grade 3 or Suspected Grade 4 Reaction for Substudy B

If a Grade 3 local reaction (Section 8.3.5.2), systemic event (Section 8.3.5.3), or fever (Section 8.3.5.4) is reported in the reactogenicity e-diary, a telephone contact should occur to ascertain further details and determine whether a site visit is clinically indicated. If a suspected Grade 4 local reaction (Section 8.3.5.2), systemic event (Section 8.3.5.3), or fever (Section 8.3.5.4) is reported in the reactogenicity e-diary, a telephone contact or site visit should occur to confirm whether the event meets Grade 4 criteria.

A site visit must be scheduled as soon as possible to assess the participant unless any of the following is true:

- The participant is unable to attend the unscheduled visit.
- The local reaction/systemic event is no longer present at the time of the telephone contact.
- The participant recorded an incorrect value in the reactogenicity e-diary (confirmation of a reactogenicity e-diary data entry error).
- The PI or authorized designee determined it was not needed.

This telephone contact will be recorded in the participant's source documentation and the CRF.

If the participant is unable to attend the unscheduled visit, or the PI or authorized designee determined it was not needed, any ongoing local reactions/systemic events must be assessed at the next study visit.

During the unscheduled visit, the reactions should be assessed by the investigator or a medically qualified member of the study staff, such as a study physician or a study nurse, as applicable to the investigator's local practice, who will:

- Measure body temperature (°F/°C).
- Measure minimum and maximum diameters of redness (if present).
- Measure minimum and maximum diameters of swelling (if present).
- Assess injection site pain (if present) in accordance with the grades provided in Section 8.3.5.2.

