3.1.4. Adverse Events

Standard algorithms for handling missing AE dates and missing AE severity will be applied as described in the Pfizer Vaccine data standard rules. AEs will be collected from informed consent signing through 4 weeks following vaccination (Visit 4).

The following derivations will be included for each participant:

- Any AE reported.
- Any related AE reported.
- Any immediate AE (acute reactions were assessed for at least 30 minutes after study intervention administration).
- Any severe AE.
- Any life-threatening AE.
- Any AE leading to study withdrawal.
- Any AE leading to death.
- Any AESI.
 - A confirmed diagnosis of influenza.
 - A confirmed diagnosis of myocarditis or pericarditis occurring within 4 weeks after vaccination.
 - Confirmed COVID-19 diagnosis through the end of the study (clinical signs/symptoms and positive SARS-CoV-2 NAAT or rapid antigen test result).

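### Nonserious COVID-19 and influenza AESIs outlast the 4-week AE collection that is meant to capture them, and Substudy B gives conflicting instructions for Visit 205

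*Protocol*

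**What the plan says.** **AESI windows.** Protocol Section 8.4.7 lists confirmed COVID-19 in both substudies. For Substudy B the window is "Confirmed COVID-19 diagnosis after Visit 201 through the end of the study", with Group 12 excluded. Confirmed influenza is listed with no time limit. Myocarditis/pericarditis counts for 4 weeks in Substudy A and 6 weeks in Substudy B. Menstrual cycle disturbances are an AESI in Substudy B only, and Sections 10.12.8.11 and 10.12.8.13 follow them for 6 months. Section 8.4.7 gives AESIs no collection period of their own. They are reported as AEs or SAEs under Sections 8.4.1 to 8.4.4.

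**Collection windows.** For Substudy B, Section 8.4.1 collects AEs from consent "through and including Visit 204", and adds "any AEs occurring up to 48 hours after the blood draws at Visit 204 in Substudy B". Only SAEs continue to about 6 months. Footnote f of the Substudy B schedule (Section 10.12.1) agrees: "AEs are collected from the completion of informed consent through Visit 204". Substudy A follows the same pattern, ending at Visit 4, with the 48-hour rule applied to the Visit 4 and Visit 5 draws.

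**Visit 205.** Section 10.12.8.1 lists, among assessments that must be done at the telehealth visit, "Review and record any AEs and SAEs since the last contact". The Visit 205 procedures in Section 10.12.8.9.6 say only "Record SAEs as described in Section 8.4.1". The schedule row is marked at Visit 205 for AEs and SAEs as appropriate, but its footnote ends AEs at Visit 204.

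**SAPs.** The Substudy A SAP, Section 3.1.4, defines one AESI as "Confirmed COVID-19 diagnosis through the end of the study". Its Section 6.1.2.2 then summarizes AESIs in the manner of the main AE analysis, which Section 6.1.2.1 runs to 4 weeks. The Substudy B SAP analyses AEs to 4 weeks and names no AESI summary.

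**The concern.** An AESI window has meaning only if someone asks about the event throughout it. Section 8.4 ties the questioning of participants about AEs to the active collection period, and for nonserious events that period ends at the 4-week visit. A nonserious COVID-19 or influenza case in month 3 is an AESI by definition, yet no undisputed instruction tells the site to ask about it. Whether it is recorded depends on the participant volunteering it, or on which Visit 205 text the site follows.

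The practical stake is signal review. Section 8.4.7 has the sponsor compare aggregate AESI counts with what would be expected from epidemiological or other data. If nonserious cases go unsolicited for most of the stated window, the count tends to fall below an external rate defined over the full window. Differing site practice would add variation unrelated to the vaccines.

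**Working it through.** The plan gives no figure to reproduce here. The check compares stated windows and then does day arithmetic.

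**Step 1. Each AESI against its route to the database (Substudy B unless noted).**

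| AESI | Stated window | Route after Visit 204 |
|---|---|---|
| COVID-19, nonserious (both substudies) | End of study | Substudy B: only the broader wording of Section 10.12.8.1. Substudy A: only the 48 hours after the Visit 5 draw |
| Influenza, nonserious (both substudies) | None stated | As above |
| Myocarditis/pericarditis | 6 weeks | SAE to 6 months under Section 10.12.8.10; AE or SAE, as the case warrants, under Section 10.12.8.12 |
| Menstrual disturbance | 6 months | Recorded on the CRF if the participant reports symptoms |

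Section 8.4.7 points to Section 10.12.8.12 for myocarditis/pericarditis, not to Section 10.12.8.10, which contains the SAE requirement. In Substudy A the 4-week myocarditis/pericarditis window matches AE collection, so no gap arises there.

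**Step 2. Time outside nonserious AE collection.** From the Substudy B schedule, Visit 204 falls at day 26 to 30 and Visit 205 at day 175 to 189. Let E be the last day of nonserious AE collection (Visit 204 day plus 0 or 2 days for the 48-hour rule) and W the end of the AESI window. The uncovered share is (W − E)/W.

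For COVID-19, with W taken as Visit 205:
- E = 26: 149/175 = 85.1%; 163/189 = 86.2%
- E = 28: 147/175 = 84.0%; 161/189 = 85.2%
- E = 30: 145/175 = 82.9%; 159/189 = 84.1%
- E = 32: 143/175 = 81.7%; 157/189 = 83.1%

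The gap is 143 to 163 days, or 82% to 86%. The top of that range leaves out the 48-hour extension; with it (E = 28 to 32) the range is 82% to 85%.

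Substudy A has the same visit days (Visits 4 and 6) and two more covered days after the Visit 5 draw. With E = 28 to 32 the gap runs from 143 − 2 = 141 days (141/175 = 80.6%) to 161 − 2 = 159 days (159/189 = 84.1%).

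For myocarditis/pericarditis in Substudy B, W = 42. The part of the window after nonserious AE collection runs from 42 − 32 = 10 days (23.8%) to 42 − 26 = 16 days (38.1%). This matters only where a case is not handled as an SAE.

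**Step 3. Analysis windows.** Sections 10.12.8.10 and 10.12.8.12 require evaluation of cardiac symptoms for 6 weeks in Substudy B. Protocol Section 10.12.9.3.5 and Substudy B SAP Sections 6.4.1 and 6.5 summarize participants with such symptoms within 4 weeks only. Data from symptoms first reported in weeks 5 and 6 are required but fall outside those summaries.

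**The case against.** The strongest reply is that collecting nonserious AEs for 4 weeks and SAEs for 6 months is a deliberate scheme, stated consistently in Section 8.4.1 and both schedules. On this view the telehealth bullet is loose drafting: it refers to Section 8.4 and the schedule, and its list ends by pointing to Section 10.12.8.9.6, all of which limit AEs or list SAEs. AESI rates are also not an objective in either substudy.

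Much of this stands, and it rules out several stronger readings that a reader might infer:

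- **That myocarditis/pericarditis after week 4 is lost.** Section 10.12.8.10 makes any diagnosis an SAE, and SAEs are collected to 6 months. What remains is the conflict with Section 10.12.8.12.
- **That menstrual disturbances are lost.** They have their own evaluation and CRF recording to 6 months. The weakness is reliance on the participant raising them, since Section 10.12.8.9.6 prompts for SAEs only at the one planned contact after Visit 204.
- **That planned AESI proportions to end of study are wrong.** The Substudy B SAP plans none. The Substudy A SAP can be read as summarizing AESIs over 4 weeks, which matches collection. The fault there is that its definition and its summary period differ without explanation.
- **That about 4 of 26 weeks (15%) of collection means 85% of events missed.** These are shares of calendar time, and the documents give no basis for a count of missed events.
- **That sites will diverge at Visit 205.** The text permits it; nothing shows it.

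The reply does not explain why Section 8.4.7 sets an end-of-study window for COVID-19 and then sends it to a procedure that stops at 4 weeks for nonserious cases. Nor do the cross-references in Section 10.12.8.1 cure its bullet, because they lead to text that contradicts it.

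**Conclusion.** The concern holds in a limited form. Nonserious COVID-19 (both substudies, Group 12 excluded in Substudy B) and nonserious influenza are AESIs beyond the 4-week visit but are not systematically solicited after about day 28 to 32. For COVID-19 in Substudy B that is 82% to 86% of the time to Visit 205. This assumes visits within their scheduled windows and takes the final contact as the end of the COVID-19 window. Applying the same share to influenza further assumes that its unstated window also runs to that contact.

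Two further contradictions in Substudy B need reconciling: Section 10.12.8.1 against Section 10.12.8.9.6 and footnote f on Visit 205, and Section 10.12.8.10 against Section 10.12.8.12 on reporting myocarditis/pericarditis. The 4-week cardiac-symptom summaries also fall short of the 6-week evaluation and AESI window. The effect is on routine safety review. The primary safety endpoints, AEs to 4 weeks and SAEs to 6 months, are collected as defined.

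**What to change.** - Reconcile Section 8.4.7 with Section 8.4.1 and both schedule footnotes so that AESIs are collected over their stated windows whether or not serious. State a window for influenza. Add an AESI question, including menstrual symptoms in Substudy B, to the existing 6-month contact.
- Make Sections 10.12.8.1 and 10.12.8.9.6 and footnote f give one instruction for Visit 205.
- Reconcile Sections 10.12.8.10 and 10.12.8.12, and check that Section 8.4.7 cites the text that governs.
- In the Substudy A SAP, state the period each AESI summary covers, since Section 3.1.4 and Sections 6.1.2.1 and 6.1.2.2 now differ.
- In Protocol Section 10.12.9.3.5 and Substudy B SAP Sections 6.4.1 and 6.5, align the 4-week cardiac-symptom summaries with the 6-week window.

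The cost is protocol and SAP wording and slightly longer 6-month calls. No added visits, samples or participants are needed.
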